# 5.2 Post-Surgery/Adjuvant Therapy

 Includes weight, BSA, and vital signs (temperature, blood pressure, pulse rate, and). Following the initial presurgery dose, for subsequent doses, the post dose vitals and 1-hour observation period will not be required unless a subject experiences an infusion-related reaction. Vital signs will be measured within an hour prior to start of study drug administration, at 30 minutes during the infusion (± 5 minutes), at the end of infusion (+ 5 minutes). If needed, vital signs will be done at 30 and 60 minutes (± 5 minutes each) post-infusion. If the infusion takes longer than 60 minutes, blood pressure and pulse measurements should follow the principles described here or more frequently if clinically indicated.

 Adjuvant treatment (cycle 1 day 1) will resume approximately 14 days (+/- 7 days) after surgery, once the surgical wound has healed.

 Will be done every other week while on adjuvant treatment.

 Will be done prior to each cycle (monthly) while on adjuvant treatment.

 If patients are unable to start treatment within 21 days of the post-surgical imaging, then repeat imaging with

enhanced MRI or CT scan should be performed prior to initiation of adjuvant therapy. During adjuvant treatment, contrast-enhanced MRI or CT scan will be done approximately every 2 cycles or 8 weeks (prior to each odd cycle). If there is no progression of disease, patients will continue on treatment for up to 24 months. If a patient has disease progression (as defined in section 6.4) or clinical decline and undergoes further surgery but is found to have no pathologic evidence of significant tumor, the patient may then re-start treatment.

-  Thyroid function tests will be done every 2 cycles (approximately every 2 months) during treatment. TSH will be done each time; free T3 and free T4 only if TSH is abnormal.
-  ECGs are required within 1 hour prior to starting study treatment and at least once after the infusion is completed (anywhere from 0-3 hours) on Cycle 1 Day 1, again after approximately 16 weeks on treatment, and at the end of treatment. ECGs may be repeated at any other time point if clinically indicated. ECGs recorded during the treatment phase will be single tracing. Twelve-lead ECGs will be obtained after the subject has been resting in a supine position for at least 5 minutes in each case.

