### 6.2 Secondary Endpoints

- 1. To evaluate the safety of either Tremelimumab or MEDI4736 alone and in combination for patients with recurrent GBM. The endpoints will be the number, frequency, and severity of adverse events (as defined by the NCI Common Terminology Criteria for Adverse Events or CTCAE version 4.03). Only patients who have been administered at least one dose of investigational drug will be evaluable for this endpoint.
- 2. To determine post-surgery, the time to progression (per Modified RANO criteria and iRANO criteria see below) for patients treated with either Tremelimumab or MEDI4736 alone and in combination of both. This will be defined as the number of months from the time of first dose of study treatment until progression of disease or death by any cause. Only patients who have been administered at least one dose of investigational drug and undergone surgery will be evaluable for this endpoint.
- 3. To determine post-surgery the overall survival for patients treated with Tremelimumab or MEDI4736 alone and in combination of both. This will be defined as the number of months surviving from the time of first dose of study treatment until death by any cause. Only patients who have been administered at least one dose of investigational drug and undergone surgery will be evaluable for this endpoint.
- 4. To assess post-surgery, the MRI changes in patients treated with either Tremelimumab or MEDI4736 alone and in combination of both. Only patients who have been administered at least one dose of investigational drug, undergone surgery, and have undergone at least one post-surgery disease assessment will be evaluable for this endpoint.

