# 6.4 Response Assessment (Modified RANO criteria)

The response to immunotherapy may differ from the typical responses observed with cytotoxic chemotherapy including the following (Wolchok et al 2009, Nishino et al 2013):

- Response to immunotherapy may be delayed
- Response to immunotherapy may occur after PD by conventional criteria
- The appearance of new lesions may not represent PD with immunotherapy
- SD while on immunotherapy may be durable and represent clinical benefit

Based on the above-described unique response to immunotherapy and based on guidelines from regulatory agencies, e.g., European Medicines Agency's "Guideline on the evaluation of anticancer medicinal products in man" (EMA/CHMP/205/95/Rev.4) for immune modulating anticancer compounds, the study use a modified RANO criteria to define PD:

Progressive disease post-baseline is defined as one or more of the following:

- New contrast-enhancing lesion outside of radiation field on decreasing, stable, or increasing doses of corticosteroids.
- Increase by > 50% (modified from >25% according to published RANO criteria) enhancement from the first post-surgical scan, or a subsequent scan with smaller tumor size, and the scan 8 weeks or later on stable or increasing doses of corticosteroids.
- Clinical deterioration not attributable to concurrent medication or comorbid conditions is sufficient to declare progression on current treatment.

Treatment with MEDI4736, Tremelimumab or both would continue between the initial assessment of progression and confirmation for progression. In addition, subjects may continue to receive MEDI4736, Tremelimumab or both beyond confirmed PD in the absence of clinically significant deterioration and if investigators consider that subjects continue to receive benefit from treatment.

As a secondary measure, for all response assessments, iRANO will be used for assessment.

RANO and iRANO criteria (iRANO= immunotherapy Response Assessment in Neuro-Oncology)						
	Response	Malignant glioma	Low-grade glioma	Brain metastasis		

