#### 10.3 Sample Size, Accrual and Data Analyses Plans

There will be three groups of patients, one group on each agent alone and one group treated with the combination agent. There will be 10 patients per group for a total of 30 patients. These 30 patients must be evaluable for the primary endpoint, meaning that they must have undergone surgery and their blood and tissue samples are available at both the pre- and post-surgery times. In order to attain 10 evaluable patients in each arm, a total of 45 patients will be accrued to the study. Sample sizes of 10 per group allow for the estimation of the proportion of responders in evaluable patients to be within 31% of its true value with 95% confidence. Mean change will be compared between arms. Using standard deviations of change, a sample size of 10 per group will allow the detection of differences of 1.25 standard deviations between groups with 80% power assuming a two-tailed test and a Type I error rate of 5%.

Immunologic measures will be summarized over the three or more time points (pre-treatment, following first treatment/pre-surgery, post-surgery) and changes in these measures will be assessed using repeated measures analysis of variance or Cochran's Q, followed by the paired t-test or the signed rank test for pairwise comparisons using Bonferroni corrections. Safety of the agents alone or in combination will be assessed by summarizing the frequency of adverse events by type, timing, grade and attribution. Response criteria will be based on RANO (including upcoming Immunologic RANO criteria) but since all patients will be post-surgery, the degree, if any, of

residual disease will vary. A patient is evaluable for efficacy if they have undergone at least one follow-up MRI after adjuvant therapy. Immunologic changes will be correlated with MRIs in a descriptive fashion. The secondary endpoint of progression-free survival as well as overall survival will be analyzed using Kaplan-Meier curves. Immunologic changes of T-cells and PDL1 levels will be correlated to survival outcomes using Cox regression analysis. MRI changes will be summarized using means or proportions and statistically analyzed using the signed rank test.

**Performance Status:** Patients will be graded according to Karnofsky Performance Status (KPS)(see appendix C).

**Evaluation of toxicity.** All patients will be evaluable for toxicity from the time of their first treatment as per NCI CTCAE version 4.03

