**Time to Progression:** From date of first treatment to the date of first observation of definitive progressive disease, non-reversible neurologic progression or increasing steroid requirements (applies to stable disease only), death due to any cause, or early discontinuation of treatment. Patients not reaching the progression endpoint at last follow-up will be censored at that time.

**Time to Death**: From date of first treatment to date of death due to any cause. Patients alive at last follow-up will be censored at that time.

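### Sections 10.3 and 6.2 give conflicting evaluability rules; applied to time to progression and survival, the 10.3 MRI rule would exclude patients with no scan on adjuvant therapy and bias both upward

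*Combined protocol and SAP*

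**What the plan says.** Section 6.2 sets evaluability endpoint by endpoint. For time to progression (item 2) and overall survival (item 3) it says: "Only patients who have been administered at least one dose of investigational drug and undergone surgery will be evaluable for this endpoint". Only item 4, MRI change, asks for imaging: treated patients must have "undergone surgery, and have undergone at least one post-surgery disease assessment will be evaluable for this endpoint".

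Section 10.3 has a different rule. After the sentence on RANO response criteria and residual disease it says: "A patient is evaluable for efficacy if they have undergone at least one follow-up MRI after adjuvant therapy". The word efficacy is not tied to a named endpoint. Two sentences later the same paragraph says: "The secondary endpoint of progression-free survival as well as overall survival will be analyzed using Kaplan-Meier curves". No analysis set is named there.

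The event definitions do not depend on a scan. At the end of 10.3, time to progression runs from first treatment, and its events include "death due to any cause, or early discontinuation of treatment". Time to death runs "From date of first treatment to date of death due to any cause". Section 6.4 adds: "Clinical deterioration not attributable to concurrent medication or comorbid conditions is sufficient to declare progression on current treatment".

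**The concern.** Two rules can be read as covering the same endpoints, and nothing says which governs. Section 10 defines evaluability three times (primary endpoint, efficacy, toxicity), so an analyst working from that section alone finds no other set for the Kaplan-Meier curves.

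If the MRI rule is used for those curves, a patient must stay in follow-up long enough to be scanned on adjuvant therapy before being counted, while the clock has been running since first dose. The patients removed are among the earliest failures, and the number removed could differ by arm if early toxicity or decline differs. The trial is open-label with 10 to 15 patients per arm, so leaving the choice of set open until outcomes are known is itself a weakness. The Cox analyses of survival inherit the same ambiguity, because 6.3 gives the exploratory endpoint the one-dose-plus-surgery rule.

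**Working it through.** **Plan's own figures.** None is stated for time to progression or survival. The 10.3 figures rest on 10 evaluable patients per arm and reproduce: 1.96 × √(0.25/10) = 0.31, and normal-approximation power for 1.25 SD is 79.8% against the stated 80%. This point does not change them.

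**Step 1: the rules side by side, for operated patients.**

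| Course after surgery | Event? | 6.2 items 2 and 3 | 10.3, if applied |
|---|---|---|---|
| Dies with no scan on adjuvant therapy | Yes, both endpoints | In | Out |
| Clinical deterioration, no discontinuation scan | Progression (6.4) | In | Out |
| Never starts adjuvant drug | Early discontinuation is an event only in the 10.3 definition | In | Out |
| Starts adjuvant drug, declines, scanned at discontinuation | Progression | In | In |

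The last row matters: the 5.2 schedule marks tumor imaging at treatment discontinuation.

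**Step 2: when the first scheduled adjuvant scan falls.** Inputs:
- first dose to surgery: 14 days ±3 (4.2 table and 5.1 schedule);
- surgery to Cycle 1 Day 1: 14 days ±7 (5.2 footnote 2);
- Cycle 1 Day 1 to the scan before Cycle 3: 8 weeks, 56 days (5.2 footnote 5).

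Nominal: 14 + 14 + 56 = day 84, or 70 days after surgery. Range: 11 + 7 + 56 = 74 to 17 + 21 + 56 = 94. Footnote 6 of 5.1 gives ±7 for the first interval, which widens the range to 70–98.

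**Step 3: illustration of size.** The documents give no survival median for this population. Assume exponential survival from first dose with median m of 6, 8 or 10 months, and 30.4375 days per month. Surgery is then at 0.46 months and day 84 at 2.76 months, a gap of 2.30 months. Survival to day 84 stands in for having been scanned.

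- Operated patients dying between surgery and day 84: 1 − 2^(−2.30/m).
- Median from first dose in the 6.2 set (alive at surgery): m + 0.46.
- Median from first dose in day-84 survivors: m + 2.76.

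| Assumed m (months) | Die before day 84 | Per 15 operated | Median, 6.2 set | Median, day-84 survivors | Change |
|---|---|---|---|---|---|
| 6 | 23% | 3.5 | 6.5 | 8.8 | +36% |
| 8 | 18% | 2.7 | 8.5 | 10.8 | +27% |
| 10 | 15% | 2.2 | 10.5 | 12.8 | +22% |

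The shift is 2.3 months at every assumed median, because the exponential has no memory. Six-month survival moves from 52.7% to 68.8% at m = 6, from 61.9% to 75.5% at m = 8, and from 68.1% to 79.9% at m = 10.

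**The case against.** The strongest reply is that the 10.3 sentence concerns radiographic response only. It follows the RANO sentence and precedes the one correlating immunologic changes with MRIs. Time to progression and survival have their own rules in 6.2, which Appendix D records as a deliberate endpoint-by-endpoint addition, and their own definitions at the end of 10.3 with no MRI condition. Specific rules would normally prevail. This stands as a plausible reading, so the loss is conditional.

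The reply does not remove the conflict. Even for response and MRI change, 10.3 disagrees with 6.2 item 4: the post-operative scan within 72 hours could count as a post-surgery assessment but is not a scan after adjuvant therapy. Section 10.3 also says MRI where the schedule allows CT.

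Two further objections stand in part. Entry requires a life expectancy of at least 12 weeks, KPS of at least 70 and resection candidacy, and day 84 is exactly 12 weeks, so a constant hazard probably overstates early deaths. The 6.2 set also leaves out treated patients who never reach surgery, so it is not an all-treated analysis either.

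**Conclusion.** The conflict is in the current text and should be fixed. If 10.3 governs the time-to-event endpoints, it creates immortal-time bias. Under the stated assumptions the shift is about 2.3 months in median survival, +36% to +22% for assumed medians of 6 to 10 months. These figures illustrate the mechanism and do not predict the trial's results.

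A reader might infer more than the documents support:
- **That everyone who dies or declines before about week 12 drops out of the efficacy results.** The plan does not say that 10.3 overrides 6.2, and a declining patient who is scanned at discontinuation meets even the 10.3 rule.
- **That the inflation is 2.8 months (8 to 10.8, +34%).** That compares day-84 survivors with all patients from first dose. The 6.2 set is already conditioned on reaching surgery, so the MRI rule adds 2.3 months.
- **That early progression measures the loss.** With an assumed median time to progression of 2 to 4 months, 62% to 38% would have progressed or died by day 84, but many of those would have a scan and remain evaluable. The number without one is unknown.

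The affected endpoints are secondary and have no stated power, and the primary T-cell endpoint is untouched. This is a should-fix.

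**What to change.** In 10.3, limit the MRI sentence to radiographic response and MRI change, and align it with 6.2 item 4: say whether the post-operative scan counts and whether CT is accepted. Add that time to progression and overall survival include every patient in the 6.2 set whether or not a follow-up MRI was done, and that death or clinical progression before the first adjuvant scan is an event. Report by arm the number of patients with no scan on adjuvant therapy.

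The cost is a few sentences. Sample size, visits and treatment do not change. Reported medians may be less favourable than under the MRI rule.

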## 2.2 Secondary Objectives & Endpoints

- 2.2.1 To evaluate the safety of either Tremelimumab or MEDI4736 alone and in combination in patients with recurrent GBM. The endpoints will be the number, frequency, and severity of adverse events (as defined by the NCI Common Terminology Criteria for Adverse Events or CTCAE version 4.03).
- 2.2.2 To determine post-surgery, the time to progression(per Modified RANO criteria and iRANO criteria see below) for patients treated with either Tremelimumab or MEDI4736 alone and in combination of both, This will be defined as the number of months from the time of first dose of study treatment until progression of disease or death by any cause.
- 2.2.3 To determine post-surgery the overall survival for patients treated with Tremelimumab or MEDI4736 alone and in combination of both. This will be defined as the number of months surviving from the time of first dose of study treatment until death by any cause.
- 2.2.4 To assess post-surgery, MRI changes in patients treated with either Tremelimumab or MEDI4736 alone and in combination of both.

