#### 4.6 Duration of Follow Up

All subjects will be followed for survival for up to 2 years/24 months from stopping study treatment. Subjects who decline to return to the site for evaluations will be offered follow-up by phone every 8-16 weeks as an alternative.

Note that patients who discontinue treatment permanently for any reason other than progression will be followed for evidence of tumor response and disease status.

Any patient who withdraws their consent, will be considered as an early discontinuation, and may be replaced if this occurs before they have received the first dose of treatment. Patients who withdraw consent but receive at least one dose of treatment will be evaluable for toxicity even if they are not fully evaluable for response. The accrual goal has been set to allow up to 45 patients to be enrolled in order to allow for early discontinuations.

If a patient withdraws consent, no further treatment or study-specific testing will be completed. The primary reason for a patient's withdrawal from the study is to be recorded in the source documents. All patients will be followed until death or 2 years/24 months from stopping treatment.

Subjects who are permanently discontinued from further receipt of investigational product, regardless of the reason (withdrawal of consent, due to an AE, other), will be identified as having permanently discontinued treatment.

Subjects who are permanently discontinued from receiving investigational product will be followed for safety for 30 days post last-dose visit including the collection of any protocol-specified blood specimens, unless consent is withdrawn or the subject is lost to follow-up or enrolled in another clinical study. If a subject is enrolled in another clinical study, they will be followed until all AEs are resolved or stable. If enrolled onto another clinical study, it is not necessary to follow the subject for survival or progression.

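### Section 10.3 counts early discontinuation of treatment as a time-to-progression event, while Sections 2.2.2 and 6.2 count only progression or death

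*Combined protocol and SAP*

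**What the plan says.** Section 2.2.2 gives time to progression (by modified RANO and iRANO) as "defined as the number of months from the time of first dose of study treatment until progression of disease or death by any cause". Section 6.2, item 2, repeats this and sets the population: "Only patients who have been administered at least one dose of investigational drug and undergone surgery will be evaluable for this endpoint".

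Section 10.3, under Time to Progression, starts the clock at first treatment and stops it when progressive disease is definitive or when one of these further items occurs, whichever comes first: "non-reversible neurologic progression or increasing steroid requirements (applies to stable disease only), death due to any cause, or early discontinuation of treatment". Its only censoring rule is "Patients not reaching the progression endpoint at last follow-up will be censored at that time". The same section names the endpoint differently: "The secondary endpoint of progression-free survival as well as overall survival will be analyzed using Kaplan-Meier curves".

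On follow-up, Section 4.6 states that "patients who discontinue treatment permanently for any reason other than progression will be followed for evidence of tumor response and disease status". Footnote 11 to the Section 5.2 schedule continues follow-up for undocumented progression every 8 to 16 weeks off treatment. Section 7.3.1 also assumes that tumor assessments go on after a stop for other reasons.

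The term has a second use. Section 4.6 says "Any patient who withdraws their consent, will be considered as an early discontinuation", and Section 4.8 applies the same label to patients who leave before surgery. For treatment stops in general, Section 4.6 uses another label: subjects, "regardless of the reason (withdrawal of consent, due to an AE, other), will be identified as having permanently discontinued treatment".

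**The concern.** One endpoint has two event lists. A patient who stops for toxicity while progression-free, and progresses months later, has an event at the stop date under Section 10.3 and at the progression date under Sections 2.2.2 and 6.2. If there are such patients, an analyst working from Section 10.3 and one working from Section 6.2 will draw different curves from the same data.

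The literal Section 10.3 version is time to treatment failure, reported under the name of progression-free survival. It also sets aside follow-up that the protocol plans to collect. The error has one direction: adding events that are neither progression nor death can only lower the curve. The dates may be used again, because Section 9.2 plans to separate responders from non-responders by progression-free and/or overall survival.

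A lesser point sits in the same sentence. Section 10.3 makes rising steroid requirements in stable disease an event, and the definition of progressive disease in Section 6.4 has no criterion based on steroids alone.

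**Working it through.** The plan states no event count, hazard ratio or power for this endpoint, so there is no figure of its own to reproduce. The conflict is a matter of text; the arithmetic only illustrates its size.

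**Text, side by side**

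| Occurrence | Sections 2.2.2 and 6.2 | Section 10.3, literal |
|---|---|---|
| Progression | event | event |
| Death, any cause | event | event |
| Stops drug without progression | not an event; followed on | event at stop date |
| Rising steroids, stable disease | not listed; no steroid-only criterion in 6.4 | event |
| Non-reversible neurologic progression | largely covered by clinical deterioration in 6.4 | event |

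The last row is not a real conflict.

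**Size on the literal reading**

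Let f be the share of first events that are non-progression stops. Assume constant hazards: L for progression or death, and g for stops, so f = g/(L + g). Then:

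- true median = ln 2 / L
- composite median = ln 2 / (L + g) = (1 − f) × true median
- composite curve at the true median = 0.5^(1/(1 − f))

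Inputs for f, used as proxies:

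- Low: Section 1.3.3 lists MEDI4736 monotherapy discontinuations of 7 + 5 + 2 + 2 + 2 + 2 = 20. Over the 393 subjects in the 10 mg/kg cohort, 20/393 = 5.1%. This assumes no overlap and covers only events seen in 2 or more subjects.
- High: Section 1.4.2 reports 27/102 = 26.5% stopping for adverse events in the NSCLC combination study.

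Both are shares of patients, not of first events, and come from other tumor types.

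| f | median ratio | curve at true median |
|---|---|---|
| 0.051 | 0.949 | 0.5^(1/0.949) = 0.48 |
| 0.265 | 0.735 | 0.5^(1/0.735) = 0.39 |

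**Against sampling error**

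Take one arm with true median 1, exponential times and no censoring. The Kaplan-Meier median is then the 5th ordered time at n = 10 and the 8th at n = 15.

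- n = 10: mean = (1/10 + 1/9 + 1/8 + 1/7 + 1/6)/ln 2 = 0.931; SD = √(1/10² + … + 1/6²)/ln 2 = 0.42
- n = 15: mean = (1/15 + … + 1/8)/ln 2 = 1.05; SD = √(1/15² + … + 1/8²)/ln 2 = 0.38

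The shift is f × mean, so:

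| | n = 10 | n = 15 |
|---|---|---|
| f = 0.051 | 0.051 × 0.931 / 0.42 = 0.11 SD | 0.051 × 1.05 / 0.38 = 0.14 SD |
| f = 0.265 | 0.265 × 0.931 / 0.42 = 0.59 SD | 0.265 × 1.05 / 0.38 = 0.73 SD |

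**Narrow reading**

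If the term means what it means in Sections 4.6 and 4.8, patients who leave before surgery are already outside the endpoint under Section 6.2. What remains is a patient who withdraws consent after surgery and is scored as an event instead of censored. If there is none, the effect is zero. The documents give no rate for this.

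**The case against.** The best defense is the narrow meaning. Sections 4.6 and 4.8 use early discontinuation for consent withdrawal or leaving before surgery, and Section 4.6 has a different label for stopping drug. On that view Section 10.3 touches very few patients. This stands as a possible reading, but Section 10.3 adds the words that tie the term to treatment, and nothing in the documents settles it.

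One might also say that discontinuation was meant as a censoring reason. The text does not allow that: it sits in the event list, and the censoring sentence covers only last follow-up.

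A third defense is scale. The endpoint is secondary, arms have 10 to 15 patients, and the shift is below one sampling SD throughout the range examined. That is fair and limits the weight of the point. It does not excuse two definitions, since the shift is systematic and avoidable.

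Three stronger readings are tempting and not supported:

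- A reader might treat the steroid item as a second contradiction of equal weight, because the general RANO table asks for stable or decreasing steroids in stable disease and marks steroids as not applicable for progression. However, Section 6.4 says that the study's modified criteria define progression. What can be said is that those criteria contain no steroid-only item. The parenthesis about stable disease may also cover neurologic progression. This needs clarifying, and the documents give no basis to size it.
- A reader might infer a biased comparison against the combination arm, if stops are commoner there. No between-arm test of this endpoint is planned, and the documents give no discontinuation rates for these arms.
- A reader might say that the two curves must differ. They differ only if someone stops without progression or has a steroid-only event.

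**Conclusion.** The conflict is real and in current text. Section 10.3 lists early discontinuation of treatment as an event; Sections 2.2.2 and 6.2 do not; the follow-up rules and the progression-free survival label agree with the latter. Followed literally, Section 10.3 biases the curve downward whenever a patient stops without progression.

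The illustrated shortening of the median by 5% to 26.5% rests on constant hazards and on discontinuation shares borrowed from other tumor types. It shows scale and does not predict this trial. On the narrow reading, only consent withdrawals after surgery are affected. The steroid wording is a lesser inconsistency of unknown size.

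The primary endpoint and the sample size do not depend on any of this. It should be fixed before analysis. Confidence is high in the textual conflict and lower in the size of its effect.

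**What to change.** In Section 10.3:

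1. Restate the Section 2.2.2/6.2 definition: first dose to progression by the modified RANO definition in Section 6.4, or death from any cause. Name iRANO as the secondary measure, as Section 6.4 does, because its confirmation and back-dating rules can give a different event date.
2. Delete early discontinuation of treatment from the event list.
3. Censor patients without progression or death at their last disease assessment. Section 4.6 allows telephone follow-up, so the last contact may include no assessment of progression.
4. Reconcile the steroid wording with Section 6.4 by stating how rising steroid requirements with otherwise stable disease are classified for this endpoint.

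The cost is a few sentences and no new data, since disease follow-up after stopping is already planned. The drawback is slightly fewer events and some possibly informative censoring, because Section 4.6 does not require progression follow-up for patients who enter another study.
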